### **3.5.1.1. Subset Reporting Interval**

A summary of adverse events occurring during a subset of the main reporting interval will be based on a shorter reporting window. This will include all TEAEs starting after or on the first dose, but doesn't start more than two days after the last dose of IP (defined as either completing the 16 weeks of treatment or discontinuing from IP earlier).

### **3.5.2. Hypoglycemic Monitoring**

Hypoglycemia AEs will be recorded in the AE Case Report Form (CRF) with details of the event captured on the Hypoglycemic Event Details CRF. Details of when these will be recorded are given in the protocol Section 8.2.5.2.

For programming purposes, the hypoglycemic AE categories are based on the following:

- Severe Hypoglycemia: Severe is checked in the severity criteria of the CRF. This assessment will be made by the PI based on the protocol definition.
- Documented Symptomatic Hypoglycemia: If (1 – Did the participant have symptoms of hypoglycemia?) Yes and (2 – Was the blood glucose measured?) Yes and result <70 mg/dL on the CRF, but hypoglycemia is not classified as severe.
- Asymptomatic Hypoglycemia: If (1) No and (2) Yes and result <70 mg/dL on the CRF, but hypoglycemia is not classified as severe.
- Probable Symptomatic Hypoglycemia: If (1) Yes and (2) No and (2b – If blood glucose was not measured, did symptoms resolve when treated with carbohydrate or glucagon?) Yes on the CRF, but hypoglycemia is not classified as severe.

### **3.5.3. Laboratory Data**

Safety laboratory tests (hematology, chemistry, urine testing and other clinical laboratory tests) will be performed as described in the protocol.

To determine if there are any clinically significant laboratory abnormalities, the safety tests will be assessed against the criteria specified in the sponsor reporting standards. The assessment will take into account whether each participant's baseline test result is within or outside the laboratory reference range for the particular laboratory parameter.

Baseline for all laboratory measurements will be defined as the result closest prior to dosing at Visit 3 (Day 1).

### 3.5.3.1. Change from Baseline Summaries

Focused change from baseline summaries (including both absolute changes from baseline and percent change from baseline, calculated separately) of the following safety laboratory endpoints will be assessed:

- Change from baseline in calcitonin to all post-dose time points as per the SOA
- Change from baseline in amylase to all post-dose time points as per the SOA
- Change from baseline in lipase to all post-dose time points as per the SOA
- Change from baseline in thyroid stimulating hormone (TSH) to all post-dose time points as per the SOA
- Change from baseline in free thyroxine (free T4) to all post-dose time points as per the SOA
- Change from baseline in lipid profile (total cholesterol, direct LDL cholesterol, HDL cholesterol and triglycerides) to all post-dose time points as per the SOA
- Change from baseline in liver function tests (ALT, AST, alkaline phosphatase, total bilirubin, bile acids and gamma-glutamyl transferase [GGT]) to all post-dose time points as per the SOA
- Change from baseline in estimated glomerular filtration rate (eGFR) to all post-dose time points as per the SOA

### 3.5.3.2. Clinical Laboratory Parameters of Interest

For the specific laboratory parameters listed in the table below, the following endpoints will be derived:

- Abnormalities defined as either a “Flag Level” or “Alert Level” as in the table below

Parameter	Flag Level	Alert Level	Conventional Units
Fasting Plasma Glucose	< 70	≤ 54	mg/dL
	≥ 270	≥ 270	
Amylase	>ULN	Pfizer standard flag for PCC	U/L
Lipase	>ULN	Pfizer standard flag for PCC	U/L
Calcitonin	>ULN	Pfizer standard flag for PCC	pg/mL

Alanine Aminotransferase	$\geq 2$ ULN	Pfizer standard flag for PCC	U/L
Aspartate Aminotransferase	$\geq 2$ ULN	Pfizer standard flag for PCC	U/L
Alkaline Phosphatase	$\geq 2$ ULN	Pfizer standard flag for PCC	U/L
Gamma Glutamyl Transferase	$\geq$ ULN	Pfizer standard flag for PCC	U/L
Total Bilirubin	$> 1.5$ ULN	Pfizer standard flag for PCC	mg/dL
Serum Total Bile Acids	$>$ ULN	Pfizer standard flag for PCC	$\mu$ mol/L

PCC – potential clinical concern

ULN – upper limit of normal as determined by the central laboratory

These endpoints will be derived using both pre and post-dose data separately. Post-dose will include all post-baseline data including unplanned readings and pre-dose will include all data from the placebo run-in defined by including all values from Visit 2 to pre-dose, including the baseline measurement and unplanned readings. Note, both pre- and post-dose populations will be from the safety analysis set (defined in Section 4).

#### 3.5.4. Vital Signs

Vital sign measurements (blood pressure and pulse rate) will be taken as detailed in the Schedule of Activities given in the protocol. The average of the triplicate measurements collected at each appropriate assessment time will be calculated for each vital sign parameter.

Baseline will be defined as the average of the triplicate measurements at the visit closest prior to dosing at Visit 3 (Day 1).

Changes from baseline for supine systolic and diastolic blood pressure and pulse rate will be calculated for each post baseline measurement.

#### 3.5.5. Electrocardiogram (ECG)

Standard 12-lead ECG (including heart rate, QT, QTcF, PR and QRS interval) will be obtained at times detailed in the Schedule of Activities given in the protocol. The average of the triplicate readings collected at each appropriate assessment time will be calculated for each ECG parameter.

Baseline will be defined as the average of the triplicate measurements at the visit closest prior to dosing at Visit 3 (Day 1).

Change from baseline for heart rate, QT, QTcF, PR and QRS interval will be calculated for each post baseline measurement.

CCI  
  
  

#### 4. ANALYSIS SETS (POPULATIONS FOR ANALYSIS)

Data for all participants will be assessed to determine if participants meet the criteria for inclusion in each analysis population prior to unblinding and releasing the database and classifications will be documented per standard operating procedures.

Population	Description
Enrolled	All participants who sign the ICD.
Randomly assigned to investigational product (IP)	All participants randomly assigned to IP regardless of whether or not IP was administered.
Evaluable	All participants randomly assigned to IP and who take at least 1 dose of IP. Participants will be analyzed according to the randomized intervention.
Safety Analysis Set	All participants randomly assigned to IP and who take at least 1 dose of IP. Participants will be analyzed according to the product they actually received.

Defined Population for Analysis	Description
Estimand Set 1A	All evaluable participants. For participants who discontinue IP and/or receive glyceimic rescue medication, all subsequent values will be censored.
CCI [REDACTED]	[REDACTED]
[REDACTED]	[REDACTED]
Estimand Set 2	All evaluable participants. Participants who receive glyceimic rescue medication and/or discontinue IP prior to Week 16 will have their Week 16 value censored (if not missing). Missing or censored values at Week 16 will be imputed as described in Section 5.3.
CCI [REDACTED]	[REDACTED]

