Any missing data (for example due to study withdrawal or laboratory failure) will have data imputed based on a MAR assumption. The population-based treatment effect will be determined for each individual time point based on the differences in the mean change from baseline in each PF-06882961 arm compared to placebo.

CCI [REDACTED]

*Estimands related to achieving HbA1c <7% at Week 16:*

A secondary estimand (Estimand 2) will be the population odds ratio of the treatment effect of achieving HbA1c <7% at Week 16 of PF-06882961 compared to placebo in the absence of glycemic rescue medication in participants while on treatment and on stable doses of background metformin and/or diet and exercise. This reflects a combination of the ‘Hypothetical’ and ‘While on treatment’ strategies as outlined in the ICH-E9 (R1) draft guidance.

Measurements after initiation of glycemic rescue medication and/or discontinuation of IP will be censored and treated as missing data. Missing data due to censoring, study withdrawal, or other reasons (eg, laboratory failure) may be imputed as outlined in the SAP. The population-based treatment effect will be the odds of achieving a HbA1c <7% at Week 16 on PF-06882961 compared to the odds of achieving this on placebo (ie, odds ratio).

*Estimands related to other endpoints:*

Estimands 3 and 4 will utilize the same approach as Estimand 1A for the associated endpoint(s).

CCI [REDACTED] Other estimands may be used for some of the primary and secondary endpoints as a means to examine the robustness of results, compare to available literature and/or be used for future study planning as needed. Details of these estimands and analyses will be presented in the SAP.

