### 9.3. Populations for Analysis

For purposes of analysis, the following populations are defined:

Population	Description
Enrolled	All participants who sign the ICD.
Randomly assigned to investigational product	All participants randomly assigned to IP regardless of whether or not IP was administered.
Evaluable	All participants randomly assigned to IP and who take at least 1 dose of IP. Participants will be analyzed according to the randomized intervention.
Safety Analysis Set	All participants randomly assigned to IP and who take at least 1 dose of IP. Participants will be analyzed according to the product they actually received.

Defined Population for Analysis	Description
Estimand Set 1A (related to estimands 1A, 2, 3, and 4)	All participants randomly assigned to IP and who take at least 1 dose of IP. For participants who discontinue IP and/or receive glycemic rescue medication, all subsequent values will be censored.
CCI [REDACTED]	[REDACTED]
[REDACTED]	[REDACTED]
[REDACTED]	[REDACTED]

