### 2.1.2. Secondary Estimand(s)

#### 2.1.2.1. Estimand Related to Achieving HbA1c <7% at Week 16

A secondary estimand (Estimand 2) will be the population odds ratio of the treatment effect of achieving HbA1c <7% at Week 16 of PF-06882961 compared to placebo in the absence of glycemic rescue medication in participants while on treatment and on stable doses of background metformin and/or diet and exercise. This reflects a combination of the 'Hypothetical' and 'While on treatment' strategies as outlined in the ICH-E9 (R1) draft guidance (1). It includes the following 4 attributes:

- Population: Defined by the inclusion and exclusion criteria to reflect participants with T2DM who are on a background of metformin and/or diet & exercise
- Variable: Response as defined by an HbA1c <7% at Week 16
- Intercurrent events: Any participant with an intercurrent event of glycemic rescue medication and/or discontinuation of IP prior to Week 16 will have all subsequent data

censored if not missing. Missing or censored values at Week 16 will be imputed (assuming missing at random [MAR]) to determine a response classification.

- Population-level summary: Odds ratio for a response between PF-06882961 (each dose considered separately) and placebo

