### 3.2. Secondary Endpoint(s)

- Response as defined by an HbA1c <7% at Week 16

This endpoint will have two levels: ‘Response’ and ‘Non-response’. The former will be based on participants having an HbA1c < 7% at Week 16, otherwise participants with a value  $\geq 7\%$  will be classed as having a ‘Non-response’. Participants with an intercurrent event of starting glycemc rescue medication and/or discontinuation of IP prior to Week 16 will have all subsequent data censored if not missing. If glycemc rescue medication and/or discontinuation of IP occurs at Week 16, the data will not be censored. The intercurrent event that occurs first during the study will take precedence for determining the censoring of data. Missing or censored values at Week 16 will be imputed as described in Section 5.3.

- Change from baseline in HbA1c at Weeks 2, 4, 6, 8 and 12
- Change from baseline in fasting plasma glucose at Weeks 2, 4, 6, 8, 12 and 16
- Change from baseline in body weight at Weeks 2, 4, 6, 8, 12 and 16

The average of the duplicate body weight readings collected at each assessment time will be calculated prior to summaries/analysis. If one of the two duplicates are missing, the non-missing value will be used, and missing values will not be imputed. Both the absolute change and %change from baseline in body weight will be calculated.

CCI

[REDACTED]

CCI [REDACTED]

[REDACTED]

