### 5.3. Methods to Manage Missing Data

Details of efficacy data to be censored is described in Sections 3.2 and 3.3.

For applicable continuous endpoints modelled with an MMRM, missing/censored values will be imputed as part of the analysis method.

In all PK data presentations (except listings), concentrations below the limit of quantification (BLQ) will be set to zero. In listings BLQ values will be reported as “<LLQ”, where LLQ will be replaced with the value for the lower limit of quantification (LLQ).

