#### 6.2.1.1. Main Analysis

In all cases the Estimand Set 2 as specified in Section 4 will be utilised.

The proportion of responses at Week 16 will be summarised descriptively by treatment as described in Section 5.2.2, where no imputation for missing values will be conducted. The proportion of responses at Week 16 will also be reported after multiple imputation for missing values as per Section 5.3.

A logistic regression model (as described in Section 5.2.4) will be applied to the response at Week 16 that will be used to estimate the treatment effect related to the secondary Estimand 2 (as described in Section 2.1.2.1), where missing values will be imputed using multiple imputation as per Section 5.3. Baseline HbA1c and strata will be included in the model.

In addition, standard SAS output will be provided to support the main statistical summary table for the logistic regression model and multiple imputation approach but will not be included in the CSR.

#### 6.2.2. Change from Baseline in HbA1c at Weeks 2, 4, 6, 8 and 12

Summaries and analysis results will be reported as per the primary analysis approach (Section 6.1.1).

#### 6.2.3. Change from Baseline in Fasting Plasma Glucose at Weeks 2, 4, 6, 8, 12 and 16

In all cases the Estimand Set 1A as specified in Section 4 will be utilised.

Absolute values and changes from baseline in fasting plasma glucose will be summarised similar to HbA1c in Section 6.1.1.1.

The analysis will be an MMRM (as described in Section 5.2.3) applied to the change from baseline at Weeks 2, 4, 6, 8, 12 and 16 that will be used to estimate the treatment effect related to the primary Estimand 3 (as described in Section 2.1.1). Results similar to HbA1c in Section 6.1.1.1 (excluding the waterfall plot) will be reported along with standard SAS output (where the latter will not be included in the CSR).

#### 6.2.4. Change from Baseline in Body Weight at Weeks 2, 4, 6, 8, 12 and 16

In all cases the Estimand Set 1A as specified in Section 4 will be utilised.

Absolute values and changes from baseline in body weight will be summarised similar to HbA1c in Section 6.1.1.1.

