## 9. APPENDICES

**Appendix 1. Summary of Efficacy Analyses**

Endpoint	Analysis Type	Population	Data Inclusion and Rules for Handling Intercurrent Events and Missing Data	Analysis Model
Change from baseline at Week 16 in HbA1c	Summary	Estimand Set 1A	GRM: Censor all values post first use DFI: Censor all values post discontinuation MV: Not imputed	N/A
	Primary analysis			MMRM
	Supplementary analyses			Emax
	CCI			
Response as defined by an HbA1c <7% at Week 16	Summary	Estimand Set 2	GRM: Censor all values post first use DFI: Censor all values post discontinuation MV: Not imputed	N/A
	Summary			N/A
	Secondary analysis			Logistic regression
Change from baseline in HbA1c at Weeks 2, 4, 6, 8 and 12	Summary	Estimand Set 1A	GRM: Censor all values post first use DFI: Censor all values post discontinuation MV: Not imputed	N/A
	Secondary analysis			MMRM
Change from baseline in fasting plasma glucose at Weeks 2, 4, 6, 8, 12 and 16	Summary	Estimand Set 1A	GRM: Censor all values post first use DFI: Censor all values post discontinuation MV: Not imputed	N/A
	Secondary analysis			MMRM
Change from baseline in body weight at Weeks 2, 4, 6, 8, 12 and 16	Summary	Estimand Set 1A	GRM: Censor all values post first use DFI: Censor all values post discontinuation MV: Not imputed	N/A
	Secondary analysis			MMRM

%Change from baseline in body weight at Weeks 2, 4, 6, 8, 12 and 16	Supplementary summary Supplementary analysis	Not applicable	GRM: Censor all values post first use DFI: Censor all values post discontinuation MV: Not imputed	N/A MMRM
CCI [Redacted]	[Redacted]	[Redacted]	[Redacted]	[Redacted]
[Redacted]	[Redacted]	[Redacted]	[Redacted]	[Redacted]
[Redacted]	[Redacted]	[Redacted]	[Redacted]	[Redacted]
[Redacted]	[Redacted]	[Redacted]	[Redacted]	[Redacted]
[Redacted]	[Redacted]	[Redacted]	[Redacted]	[Redacted]
[Redacted]	[Redacted]	[Redacted]	[Redacted]	[Redacted]
[Redacted]	[Redacted]	[Redacted]	[Redacted]	[Redacted]
[Redacted]	[Redacted]	[Redacted]	[Redacted]	[Redacted]

Abbreviations: DFI = discontinuation from IP; GRM = glyceimic rescue medication; MV = missing values (note this includes missing values produced through censoring).

[Redacted]

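### Does the Estimand Set 2 row in SAP Section 4 let HbA1c values after rescue or IP discontinuation into the responder analysis?

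*SAP*

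**What the plan says.** The analysis-set table in SAP Section 4 has one row for Estimand Set 1A and one for Estimand Set 2. The Set 1A row censors every value after IP discontinuation or rescue. The Set 2 row, which serves the responder endpoint, says that participants who are rescued and/or "discontinue IP prior to Week 16 will have their Week 16 value censored (if not missing". It adds that missing or censored Week 16 values are imputed according to Section 5.3.

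The same endpoint is covered in five other places:

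- SAP 2.1.2.1 (Estimand 2): a participant with "glycemic rescue medication and/or discontinuation of IP prior to Week 16 will have all subsequent data" censored.
- SAP 3.2: "discontinuation of IP prior to Week 16 will have all subsequent data censored if not missing". It adds that the first event governs, and that an event occurring at Week 16 itself does not lead to censoring.
- SAP Appendix 1, entry for Estimand Set 2: "GRM: Censor all values post first use DFI: Censor all values post discontinuation".
- Protocol 9.1.1 (Estimand 2): "Measurements after initiation of glycemic rescue medication and/or discontinuation of IP will be censored and treated as missing data".
- Protocol 9.3: there is no separate Set 2. Estimand 2 is assigned to "Estimand Set 1A (related to estimands 1A, 2, 3, and 4"), where all values after the event are censored.

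On where the censoring rules are to be found, SAP 5.3 states: "Details of efficacy data to be censored is described in Sections 3.2 and 3.3".

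**The concern.** Two rows of one table use different wording, which usually signals two different rules. The Set 2 row is also one that programmers will use. SAP 6.2.1.1 says of the responder analysis: "In all cases the Estimand Set 2 as specified in Section 4 will be utilised". SAP 5.3.1 imputes from all Set 2 time points up to Week 16, and the example code in SAP Appendix 4 puts Weeks 2 to 12 in the imputation model with Week 16. That code has no censoring step, so the incoming dataset decides which values enter.

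The values in question will exist. Protocol 7.1 keeps participants in the visit schedule after they stop IP, Protocol 6.5.5 does so after rescue, and HbA1c is drawn at each treatment visit.

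If the set were built from this row alone, HbA1c measured off drug or on rescue at, say, Week 8 or 12 would predict the imputed Week 16 value. The odds ratio would then move away from Estimand 2, the on-treatment effect without rescue. SAP 5.1 gives this endpoint a 1-sided 5% test for each dose, so the result would be reported as an inferential one.

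**Working it through.** No figure in the plan depends on this row, so there is none to reproduce. The check is of the text, followed by an illustration of what a misbuild could do.

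**Step 1: does the row contradict the fuller rule?** The fuller rule censors all values after the event. The Week 16 value of anyone with an event before Week 16 is one of these, so the row is true under the fuller rule. A contradiction would need the row to say that earlier post-event values are retained, or that Week 16 alone is censored. It says neither.

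**Step 2: where does the plan lead a programmer?** SAP 6.2.1.1 points to Section 4. The Set 2 row points to 5.3. Section 5.3 points to 3.2 for censoring. Section 3.2 censors all data after the event. Appendix 1 gives the same rule against Set 2 by name. The Set 2 row and Section 3.2 both limit censoring to events before Week 16, so the exception for events at Week 16 fits.

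**Step 3: which outputs could differ?**

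| Output | Week 16 value only | All post-event values |
|---|---|---|
| Primary MMRM (Set 1A) | same | same |
| Unimputed Week 16 response summary | same, as Week 16 is censored either way | same |
| Imputed response proportions | can differ | as Estimand 2 |
| Logistic odds ratios | can differ | as Estimand 2 |

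**Step 4: illustration of size.** The documents give no IP-stop rate and no attendance rate after stopping, so these are assumed.

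*Simulation A* has one active arm and placebo, 200,000 per arm. Assumed: baseline HbA1c mean 8.1, SD 0.9, clipped to 7 to 10.5; Week 16 change SD 1.0; adjacent-visit correlation 0.85; event after the Week 4, 6 or 8 visit; all visits attended; drug effect lost by Week 16 after stopping; rescue worth 0.8%. Week 16 is imputed by regression on baseline, treatment and earlier visits.

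Odds ratio = [p1/(1 − p1)] / [p0/(1 − p0)]. In the first row below, p0 = 0.164. With p1 = 0.423 under Week 16-only censoring, the ratio is (0.423/0.577)/(0.164/0.836) = 3.74. With p1 = 0.460 under full censoring it is 4.33 from unrounded proportions.

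| Scenario | Full censoring | Week 16 only | Truth | Reduction |
|---|---|---|---|---|
| Effect 1.0%, stops 25% active / 10% placebo | 4.33 | 3.74 | 4.34 | 14% |
| Effect 1.0%, stops 35% / 10% | 4.32 | 3.45 | 4.30 | 20% |
| Effect 0.5%, stops 25% / 10% | 2.12 | 1.96 | 2.12 | 8% |
| Effect 1.0%, rescue 10% placebo / 2% active | 4.37 | 4.03 | 4.35 | 8% |
| Effect 1.0%, rescue 20% / 2% | 4.33 | 3.66 | 4.32 | 15% |

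*Simulation B* has 300 six-arm trials per scenario with 67 per arm, SD 1.0% and a 0.5% effect in one arm (Protocol 9.2). Assumed: other effects 0.2, 0.8, 1.0 and 1.1%; baseline as in A but truncated; stops uniform over Weeks 1 to 10; a 4-week HbA1c onset and offset; residual correlation exp(−weeks/20). Imputation and pooling follow SAP Appendix 4 (20 imputations, 10 iterations).

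| Scenario | Top-dose odds ratio, full to Week 16 only |
|---|---|
| 25% stop, all keep attending | 7.0 to 5.2 (26% lower) |
| 25% stop, half keep attending | 6.9 to 5.9 (14% lower) |
| 25% stop, none keep attending | ratio 0.99, within simulation error |
| 10% stop, all keep attending | 11% lower |
| Stops graded 10 to 30%, all / half keep attending | 29% / 18% lower |
| Rescue only, 10% on placebo falling to 0 | odds ratios 1 to 2% lower |

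With 25% stopping and all attending, power in the 0.5% arm falls from 53% to 43%, and at the top dose from 99% to 98%. In Simulation A, where the true value is known, full censoring recovers it to within 0.02.

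**The case for a change.** The strongest case for a change is that SAP 6.2.1.1 makes Section 4 the operative definition and nothing says which section prevails if they differ. The Set 1A row shows that the authors knew how to write the full rule. Both simulations agree on direction: a literal build lowers the odds ratio. The correction would be a few words.

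What stands is that the Set 2 row is less complete than its neighbour, and that a programmer who read it and nothing else could build the wrong dataset.

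The rest does not carry. No rule of precedence is needed, because a statement about Week 16 and a statement about all later visits can both hold. Naming Week 16 is natural for an endpoint defined and modelled at that visit. The SAP version history lists Sections 2.1.2.1, 3.2 and 4 as revised together to return this estimand to the protocol's wording, which argues against a deliberate second rule.

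The simulated losses also need care. The 25% in Protocol 9.2 is drop-out, and it is what leaves about 50 completers per arm. Protocol 4.5 defines a completer by attendance through Visit 11, and Protocol 7.1 says that stopping IP is not withdrawal. Using 25% as the share who stop IP and still attend gives the figure a different meaning. The scenario closest to its stated meaning is the one in which those who stop also leave, and there the two readings agree. For rescue alone, the two simulations give reductions of 1 to 2% and 8 to 15%, so the assumptions drive the size.

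**Conclusion.** No change to the plan is called for. The Set 2 row is an incomplete summary of a rule stated in full in SAP 2.1.2.1, 3.2 and Appendix 1 and in Protocol 9.1.1 and 9.3, and the row's own reference leads to that rule by way of 5.3. An analyst who follows the SAP as written censors all HbA1c values after the first event before Week 16 and estimates Estimand 2 as intended. Aligning the row would be editorial and would alter no planned result, sample size or error rate.

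The effect on the planned analysis is nil. The reductions of 1% to 29% describe a build that the plan does not call for, and they rest on assumed stop, rescue and attendance rates that the documents do not give. The conclusion itself rests on the text alone: five statements of the full rule for this endpoint, and none that keeps post-event values.
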